11. STUDY VISITS

The overall and detailed schedule for study procedures and visits is provided in [Table 2](#).

11.1. Visit 1 (Day -35 to Day -7)

11.1.1. Informed Consent

Before the potential patient has undergone any study-related screening procedures, including any down-titration or withdrawal of medications, the nature of the study and the potential risks associated with it will be explained to the patient, and the patient will be given an opportunity to ask questions to his or her satisfaction. After the questions are answered, but before proceeding further, the patient must read and sign a written informed consent form. This signed informed consent form will be retained in the Investigator's study file, and the date the patient signed the form will be entered into the CRF. The patient will be provided with a copy of his or her signed and dated informed consent form. The patient will be required to sign all updated informed consents.

11.1.2. Screening Overview

The first study visit, Screening Visit 1, will be where the study is explained to the prospective study patient, where written informed consent will be obtained and documented, and where certain protocol-specified study procedures and assessments will be completed. Screening Visit 1 will start a variable length screening period. The length of the screening period is to be no shorter than 7 days (since the "run-in" period during which baseline diary data are collected must be at least 7 days in duration), but may be as long as 35 days in order to accommodate medication wash-out or other study requirements. For extenuating circumstances, the total duration of the Screening period may be increased to up to a maximum of 49 days with Medical Monitor approval.

If the patient does not need to complete any medication wash-out, and assuming all screening procedures have been successfully completed and initial eligibility has been confirmed, then the patient may begin the 7-day run-in period as soon as the screening visit has been completed. Yet, due to potential delays in the issuance of a final laboratory report (e.g. when a confirmatory analysis is required, typically on a urine drug screen analyte that is preliminarily positive), it is recommended that the Baseline Visit is scheduled at least 10 days from the Screening Visit. If the patient needs to complete medication wash-out prior to the start of the run-in period, the down titration schedule for the patient and the date on which the patient should start the run-in period should be provided in writing to the patient. It is acceptable if another clinic visit is deemed necessary by the Investigator before initiating the run-in period (and should be recorded as an unscheduled visit). It is important to remember that any patient with a positive urine drug screen (for a drug requiring washout) must return to the site for a repeat UDS prior to beginning their 7-day baseline data collection period. The repeat UDS for benzodiazepines must be centrally analyzed; all others may be performed on site. Patients who test positive for cannabis/THC at the screening visit but are deemed eligible to continue are not required to undergo repeat UDS testing.

11.1.3. Patient Numbering

All screened patients will be assigned a unique patient number.

11.1.4. Screening Assessments and Procedures

The following screening assessments/procedures will be completed in the following general order:

- Obtain written informed consent to participate
- Inclusion/exclusion criteria
- Demographics
- Medical history
- Confirmation that patient satisfies the 2016 Revisions to the 2010/2011 fibromyalgia diagnostic criteria (2010 American College of Rheumatology provisional diagnostic criteria/2011 self-report modification for survey and clinical research)
- Prior medication history
- Lifetime fibromyalgia pharmacotherapy history
- NRS assessment of 7-day recall of average daily pain. Patients should only continue screening if they score ≥ 4 and ≤ 9 . A score outside this range will require Medical Monitor approval in order to continue.
- Mini International Psychiatric Interview 7.0.2 – Modules A (Major Depressive Episode), C (Manic and Hypomanic Disorders), I (Alcohol Use Disorder), J (Substance Use Disorder), and K (Psychotic Disorders)
- MSI-BPD
- BDI-II. Any patient with a BDI-II total score > 24 or a response of 2 or 3 to item #9 (suicidal ideation) is not eligible for randomization.
- “Baseline/Screening” version of the C-SSRS. Any patient with C-SSRS Type 4 or 5 ideation during the preceding 6 months or any suicidal behavior during the preceding 12 months should be screen failed.
 - a. Results of the C-SSRS and BDI-II should be reviewed together at each visit to ensure (1) the patient is not experiencing suicidal ideation or worsening depression that requires intervention and (2) both scales are providing a consistent clinical picture of the patient with regard to suicidality.
- Physical examination, including vital signs, height, weight and BMI. Patients with BMI >45 must receive Medical Monitor approval prior to randomization.
- Thorough examination of the oral cavity. This examination should include a careful visual examination of the sublingual area, tongue, buccal mucosa, lips, palate and gums, aided with a tongue depressor, as well as palpation of the lips, hard palate, and

floor of the mouth. Any abnormalities should be noted on the oral cavity examination source document.

- Clinical laboratory tests
- Drug screening
- Serum pregnancy test (for women of child-bearing potential)
- 12-lead electrocardiogram
- Only those patients meeting all of the inclusion and none of the exclusion criteria will be eligible to continue. Eligible patients will:
 - a. Be instructed regarding the questions that will be asked of them on the daily diary and receive information and materials necessary to initiate their daily diary record, along with information of what they are to do if they have difficulties recording their information. Patients will be asked to start the diary that evening. Due to limitations in the reporting window, patients that are planning on international travel during the study period, or who work night shifts, should not be considered for the study.
 - b. Receive an appointment to return to the clinic for Visit 2.
 - c. Receive a schedule for down-titration (if required) of any prohibited medications to be discontinued.

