2. The patient has been diagnosed with a complex regional pain syndrome, failed back surgery syndrome, persistent or prevalent pain symptoms related to systemic disease (e.g., diabetic peripheral neuropathy, post-herpetic neuropathy), untreated hyperparathyroidism, or a history of prior surgery, trauma or other source of pain that, in the Investigator's opinion, would confound or interfere with the assessment of the patient's fibromyalgia pain or require excluded therapies during the patient's study participation.
3. The patient has any lifetime history of bipolar disorder, schizophrenia, schizoaffective disorder, or other psychotic disorder as determined at Screening either by history or by the Mini International Neuropsychiatric Interview, Version 7.0.2 (MINI 7.0.2) Module A (Major Depressive Episode), Module C (Manic and Hypomanic Episodes), and Module K (Psychotic Disorders).
4. History of or evidence for a diagnosis of borderline personality disorder (BPD) based on a score of ≥ 7 on the McLean Screening Instrument for BPD (MSI-BPD) at Visit 1 (Screening). Any patient who scores ≥ 7 on the MSI-BPD may be randomized only with Medical Monitor approval.
5. The patient is at increased risk of suicide on the basis of the Investigator's judgment, or the results of the Beck Depression Inventory-II (BDI-II) (a response > 1 to BDI-II item #9), or the results of the Columbia Suicide Severity Rating Scale (C-SSRS) conducted at Screening and Baseline (e.g., C-SSRS Type 3, 4 or 5 ideation during the preceding 6 months and any suicidal behavior within the past 12 months).
6. A BDI-II score greater than 24 at either the Screening or Baseline visit.
7. The patient has participated in any other study with TNX-102 SL.
8. Based on screening laboratory results, TSH > 1.5 times the upper limit of normal or AST or ALT > 2 times the upper limit of normal; or, in the Investigator's opinion, evidence of a clinically significant laboratory abnormality based on Screening laboratory tests or medical history.
9. Diagnosed with clinically significant and currently relevant cardiac disease (e.g., significant arrhythmia; heart block; heart failure; symptomatic coronary artery disease), recent myocardial infarction [within the past 2 years] or QTcF > 450 msec (male) or > 470 msec (female) on the screening electrocardiogram (ECG).
10. The patient has a known current clinically significant systemic infection (e.g., HIV, hepatitis).

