8.3. Patient Exclusion Criteria

Eligible patients who meet any of the following criteria during the screening period should be excluded from the study:

1. The patient has been diagnosed with infectious or inflammatory arthritis (e.g., rheumatoid arthritis, ankylosing spondylitis, psoriatic arthritis), systemic lupus erythematosus, untreated or active gout, (i.e. any acute attack within past 2 years is exclusionary), or meets criteria for other type of systemic autoimmune disease.
2. The patient has been diagnosed with a complex regional pain syndrome, failed back surgery syndrome, persistent or prevalent pain symptoms related to systemic disease (e.g., diabetic peripheral neuropathy, post-herpetic neuropathy), untreated hyperparathyroidism, or a history of prior surgery, trauma or other source of pain that, in the Investigator's opinion, would confound or interfere with the assessment of the patient's fibromyalgia pain or require excluded therapies during the patient's study participation.
3. The patient has any lifetime history of bipolar disorder, schizophrenia, schizoaffective disorder, or other psychotic disorder as determined at Screening either by history or by the Mini International Neuropsychiatric Interview, Version 7.0.2 (MINI 7.0.2) Module A (Major Depressive Episode), Module C (Manic and Hypomanic Episodes) and Module K (Psychotic Disorders).
4. History of or evidence for a diagnosis of borderline personality disorder (BPD) based on a score of ≥ 7 on the McLean Screening Instrument for BPD (MSI-BPD) at Visit 1 (Screening). Any patient who scores ≥ 7 on the MSI-BPD may be randomized only with Medical Monitor approval.
5. The patient is at increased risk of suicide on the basis of the Investigator's judgment, or the results of the BDI-II (a response > 1 to BDI-II item #9), or the results of the C-SSRS conducted at Screening (e.g., any C-SSRS Type 3, 4 or 5 suicidal ideation during the preceding 6 months and any suicidal behavior within the past 12 months) and Baseline (e.g., any C-SSRS Type 3, 4, or 5 suicidal ideation or any suicidal behavior since Screening visit).
6. A BDI-II score greater than 24 at either the Screening or Baseline visit.
7. The patient has participated in any other study with TNX-102 SL.

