11.2.2. Baseline Visit

For patients who have qualified for randomization, these assessments and procedures will be completed in the following general order:

- Confirm patient's eligibility based on the diary data collected during the preceding 7 days
- Review completed diary data with the patient
- Update medical history (with any changes noted since screening)
- Assess changes in medication history and concomitant medications
- Have the patient complete the BDI-II. If the BDI score is >24 , the patient is not eligible for randomization and should be screen failed. In addition, a score > 1 on item #9 (suicidal ideation) is exclusionary.
- Administer the "Since Last Visit" version of the C-SSRS. Any patient exhibiting Type 3, 4, or 5 suicidal ideation or any suicidal behavior since the Screening visit should be screen-failed and assessed for appropriate follow-up care.
 - a. Results of the C-SSRS and BDI-II should be reviewed together to ensure (1) the patient is not experiencing suicidal ideation or worsening depression that requires intervention and (2) both scales are providing a consistent clinical picture of the patient with regard to suicidality.
- Assess occurrence of adverse events
- Conduct a brief physical examination, including vital signs and weight
- Conduct a visual examination of the oral cavity. This examination should include a careful visual examination of the sublingual area, tongue, buccal mucosa, lips, palate and gums. Any abnormalities should be noted on the oral exam source document. It is recommended that both non-significant as well as significant findings be noted so that there is a complete and accurate baseline assessment available for comparison to findings at later visits.
- Perform urine pregnancy test (for women of child-bearing potential)
- Patient should complete the following patient-reported outcomes (PRO):
 - a. FIQR
 - b. Clinic administered assessment of pain by both 24-hour and weekly recall using 11-point (0-10) NRS scale
 - c. PROMIS scales for sleep disturbance and fatigue
 - d. CSFQ-14 female or male version, as appropriate
- Ensure that all PROs were accurately and fully completed

- Once it has been confirmed that the patient remains eligible, randomize patient via IRT Randomization System
- Dispense bottle of double-blind study drug as assigned via the IRT
- Review patient instructions regarding study drug dosing and diary completion (Section 10.2 and Section 12.2.6).

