12.3.4. Columbia- Suicide Severity Rating Scale (C-SSRS)

The C-SSRS is a questionnaire developed by researchers at Columbia University to assess and track suicide risk and behavior. This scale is intended to be used by individuals who have received training in its administration. The questions contained in the Columbia-Suicide Severity Rating Scale are suggested probes. Ultimately, the determination of the presence of suicidal ideation or behavior depends on the judgment of the individual administering the scale.

Two versions of this questionnaire will be utilized in this study. At Visit 1, the "Baseline/Screening" questionnaire will be administered, and the recall periods will be "lifetime" and "within the past 6 months" for suicidal ideation and "within the past 1 year" for suicidal behavior. Patients whose responses are indicative of suicidal ideation with intent and/or plan (e.g., Type 3, 4 or 5 suicidal ideation) within the past 6 months or a history of suicidal behavior within the past year will be excluded from participation, with recommended referral for appropriate intervention.

At all subsequent visits (Visits 2, 3, 4, 5 and 6), the "Since Last Visit" version of the questionnaire will be administered, and the recall period on this will be "since the last visit". Note that if there has been a significant change in responses indicative of increased suicide risk, appropriate intervention should be prescribed.

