14.3. Serious Adverse Events (SAEs) and Serious Adverse Drug Reactions

Any SAE that occurs at any time during the study, including a clinically significantly abnormal laboratory test result that is considered serious, must be reported to Tonix or its designee(s) so that Tonix may comply with regulatory obligations. If the SAE is life-threatening or fatal, it must be reported to Tonix or its designee(s) immediately, by facsimile and telephone. For these and all other SAEs, an SAE report form must be completed and sent by facsimile or email to Tonix or its designee(s) within 1 working day of the site's initial awareness of the event. These requirements apply equally to all patients, regardless of the study phase or the at-risk patient's treatment assignment or dosage.

A serious adverse event (experience) or reaction is any untoward medical occurrence that, at any dose:

- Results in death,
- Is life-threatening,
- Requires in-patient hospitalization or prolongation of existing hospitalization,
- Results in persistent or significant disability/incapacity,
- Is a congenital anomaly/birth defect, or
- Is an important medical event

NOTE: The term "life-threatening" in the definition of "serious" refers to an event in which the patient was at risk of death at the time of the event. It does not refer to an event that hypothetically might have caused death if it were more severe.

Medical and scientific judgment should be exercised in deciding whether expedited reporting is appropriate in other situations, such as important medical events that may not be immediately life-threatening or result in death or hospitalization but may jeopardize the patient or may require intervention to prevent one of the other outcomes listed in the definition above. *These should also usually be considered serious.* Examples of such events are intensive treatment in an emergency room or at home for allergic bronchospasm, blood dyscrasias or convulsions that do not result in hospitalization, or development of drug dependency or drug abuse. The development of C-SSRS suicidal ideation type 4 (intent) or type 5 (specific plan and intent) any time after consenting to the study should always be reported as an SAE. Additionally, since only Types 1 and 2 are allowed at Screening or Baseline, the development of C-SSRS type 3 (method but no plan or intent) after consenting should always be reported as an AE.

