11.3 Columbia Suicide Severity Rating Scale (C-SSRS)

The C-SSRS is an instrument that measures suicidal ideation and behavior, as represented by the items displayed in the table below. Frequency counts of yes/no responses to each item, and whether any suicidal ideation or behavior is present, will be summarized as described below.

The overall number of subjects with lifetime and/or current suicidal ideation (by item and category), suicidal behavior (by item and category), or self-injurious non-suicidal behavior at the screening and baseline visit will be summarized by visit and treatment group.

Additionally, the number of subjects with increase over baseline in suicidal ideation at any time point will be reported. The maximum ideation across all visits for a subject will also be summarized with counts and percentages both for all subjects and among subjects with an increase in ideation. Likewise, the count and percentage of subjects with any suicidal behavior will be reported along with a summary of the most extreme behavior each subject reported.

| Category | Items |
|----------------------|---|
| A) Suicidal Ideation | (1) Wish to be dead (2) Non-specific active suicidal thoughts (3) Active suicidal ideation with any methods (not plan) without intent to act (4) Active suicidal ideation with any some intent to act, without specific plan (5) Active suicidal ideation with specific plan and intent |
| B) Suicidal Behavior | (6) Preparatory acts or behavior (7) Aborted attempt (8) Interrupted attempt (9) Actual attempt (10) Completed suicide Suicidal Behavior present (composite of items 6-10) Non-Suicidal Self-Injurious Behavior |

A data listing of C-SSRS results will include only subjects with suicidal ideation, suicidal behavior, or self-injurious behavior without suicidal intent at any visit. For subjects with suicidal ideation, suicidal behavior, or self-injurious behavior without suicidal intent at any time, data from all visits will be displayed.

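### The Visit 1 C-SSRS step omits Type 3 ideation from a screen-failure rule that the rest of the protocol sets at Types 3 to 5

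*Protocol*

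**What the plan says.** Protocol 11.1.4 lists the Visit 1 procedures. Its C-SSRS item directs that "Any patient with C-SSRS Type 4 or 5 ideation during the preceding 6 months or any suicidal behavior during the preceding 12 months" be screen failed.

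The other texts that set an entry threshold read differently:

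- Exclusion criterion 5 in the synopsis gives as its example "C-SSRS Type 3, 4 or 5 ideation during the preceding 6 months and any suicidal behavior within the past 12 months".
- Exclusion criterion 5 in 8.3 gives, for Screening, "any C-SSRS Type 3, 4 or 5 suicidal ideation during the preceding 6 months and any suicidal behavior within the past 12 months".
- Section 12.3.4, on the Visit 1 form, excludes patients with "ideation with intent and/or plan (e.g., Type 3, 4 or 5 suicidal ideation) within the past 6 months or a history of suicidal behavior" in the past year.
- Section 11.2.2, on Visit 2, states: "Any patient exhibiting Type 3, 4, or 5 suicidal ideation or any suicidal behavior since the Screening visit should be screen-failed".
- Section 14.3 takes the limit as settled: "since only Types 1 and 2 are allowed at Screening or Baseline, the development of C-SSRS type 3 (method but no plan or intent").

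The SAP item table in 11.3 defines item 3 as "Active suicidal ideation with any methods (not plan) without intent to act".

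**The concern.** The item in 11.1.4 is the instruction a rater has in hand when scoring the Visit 1 C-SSRS, and it states an explicit screen-failure rule that is looser than the exclusion criterion it is meant to apply. Read beside the Visit 2 step, which does name Type 3, it can look deliberate, as if past Type 3 ideation were tolerated and only recent Type 3 ideation were not.

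What is at stake is patient safety and consistent eligibility across 35 to 45 sites. Some patients also withdraw existing medication after Visit 1, and section 9.1 warns that washing out certain antidepressants could destabilize patients with comorbid depression. A patient wrongly continued at Visit 1 may have begun down-titration before a later check finds the error. In addition, the rule in 14.3 that newly developed Type 3 ideation is reported as an adverse event rests on the premise that nobody enters with more than Type 2.

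**Working it through.** No arithmetic applies. The check sets side by side every place that fixes a C-SSRS threshold for entry.

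| Place in protocol | Applies at | Ideation that bars entry | Link to suicidal behavior |
|---|---|---|---|
| 11.1.4 | Visit 1 | Types 4, 5 | or |
| Synopsis, criterion 5 | Screening and Baseline | Types 3, 4, 5 | and (inside an example) |
| 8.3, criterion 5 | Screening | Types 3, 4, 5 | and (inside an example) |
| 12.3.4 | Visit 1 | Types 3, 4, 5 | or |
| 11.2.2 | Visit 2 | Types 3, 4, 5 | or |
| 14.3 | Screening or Baseline | anything above Type 2 | not addressed |

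Five of the six bar Type 3; only 11.1.4 does not. No redaction or amendment log explains the difference.

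**Test case.** Take a patient whose worst ideation in the six months before Screening was Type 3, four months ago, with no suicidal behavior in the past year and nothing since Screening.

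1. *The item in 11.1.4:* not a screen failure.
2. *Criterion 5:* excluded on the evident intent. Read literally, though, the example asks for ideation *and* behavior, and this patient has no behavior. The Baseline half of the same criterion in 8.3 uses *or*, as do 11.1.4 and 12.3.4, so *and* is a slip.
3. *Section 12.3.4:* excluded, because the parenthesis names Type 3. The descriptor in front of it, intent and/or plan, does not fit Type 3, which 14.3 and the SAP table both define as having neither.
4. *Section 14.3:* not allowed. This is unambiguous, but it sits in the adverse-event chapter.
5. *The Visit 2 C-SSRS in 11.2.2:* passes. The Since Last Visit form covers only the screening period, which 11.1.2 sets at 7 to 35 days, or up to 49 with approval. It reaches none of the six months before Screening.

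The same patient therefore passes one Visit 1 instruction and is barred by the others. Two of the texts a site would consult to settle the question, criterion 5 and 12.3.4, contain wording that could support the looser reading.

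**The case against.** The strongest reply is that eligibility is not really in doubt. The exclusion criteria govern, and the item in 11.1.4 is an incomplete list of triggers, not a statement that Type 3 is acceptable. The same Visit 1 list ends with "Only those patients meeting all of the inclusion and none of the exclusion criteria will be eligible to continue". Randomization criterion 1 (8.4) re-checks every criterion at Visit 2, and inclusion criterion 9 (8.2) requires Medical Monitor approval before the Baseline visit.

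There are also safeguards specific to suicidality. The BDI-II excludes a total above 24 or a score above 1 on item 9, at both Visit 1 and Visit 2. The C-SSRS and BDI-II must be reviewed together. Criterion 5 also excludes on the Investigator's own judgment of suicide risk. Finally, the Visit 1 form already elicits ideation over the past six months and lifetime, so a Type 3 response would be on record. The gap lies in the action rule, not in the measurement.

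Most of this stands, and it is why the matter is minor. It does not remove the inconsistency. The general check leads back to criterion 5, whose example has its own wording fault. The BDI-II measures current symptoms (12.3.3), so it would not catch every patient whose ideation lay months back. The re-check and the Medical Monitor can intercept an error, but possibly after washout has started. The two side points, *and* for *or* and the descriptor in 12.3.4, are editorial by themselves and belong here only because they weaken the text a site would fall back on.

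**Conclusion.** The concern holds. The Visit 1 C-SSRS step states the wrong threshold: it omits Type 3, which the five other entry rules bar. The intended rule is clear from those five, so this is an internal inconsistency to correct rather than a design decision to reopen.

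Its size cannot be put in numbers, because the documents give no rate of Type 3 ideation at Screening. The patients exposed are those whose worst ideation in the preceding six months was Type 3, who had no suicidal behavior in the past year, and who also pass the BDI-II limits, the Investigator's risk judgment, the general criteria check and the Medical Monitor's review. That group is probably small, but the consequence for a patient in it concerns safety. There is no effect on efficacy, sample size, power or type I error. The conclusion assumes that sites act on the step as printed; site training materials that state the full rule would reduce the risk further, but the documents do not include them.

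**What to change.** In the next protocol amendment:

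1. **Section 11.1.4:** change the ideation types in the C-SSRS item from 4 or 5 to 3, 4 or 5. Leave the look-back periods and the *or* as they are.
2. **Exclusion criterion 5, in both the synopsis and 8.3:** in the Screening example, replace *and* with *or* between ideation and behavior, to match 11.1.4 and 12.3.4.
3. **Section 12.3.4:** replace the descriptor before the parenthesis with one that fits Type 3, for example ideation with method, intent and/or plan.

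This changes a few words in four places and needs a short note to sites. Design, visit schedule and analysis stay as they are.
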